	
Secondary Objectives
 
 1. To determine the response* of the Janssen Ad26.CoV2.S vaccine in the subset of subjects who did not respond to an additional dose of the Janssen Ad26.CoV2.S vaccine in Segment I while on their maintenance immunosuppression. In this instance immunosuppression is adjusted (Segment II). 2. To determine the incidence of COVID-19 infection up to 2 years after enrollment or additional dose in all enrolled kidney transplant recipients (received Janssen Ad26.CoV2.S vaccine or not). 3. To determine the safety of an additional dose with the Janssen Ad26.CoV2.S vaccine after two or more doses of mRNA vaccine including vaccination with or without immunosuppression adjustment. 
*Response is defined as achieving an anti-SARS-CoV-2 spike protein antibody level ≥ 250 U/ml 28 days after an additional dose with the Janssen Ad26.CoV2.S vaccine.

	
Exploratory Objective
 
 1. To perform exploratory in vitro assays to better understand the mechanisms of response to COVID-19 vaccination.
Number of Subjects	Up to 1200 kidney transplant recipients at least 90 days after transplantation. 400 patients with low or no anti-SARS-CoV-2 spike protein antibody levels will receive one or two additional doses of the Janssen Ad26.CoV2.S vaccine per protocol. Approximately 800 kidney transplant recipients who had a good response to mRNA vaccines will be followed for 2 years for COVID infection and other outcomes.
Diagnosis and Main Inclusion	Kidney transplant recipient who have previously received two or more COVID-19 vaccinations (either the Pfizer or Moderna vaccines).
Study Product, Dose, Route, Regimen	
Janssen Ad26.CoV2.S, vaccine. The Janssen Ad26.COV2.s vaccine will be supplied at a concentration of 1×10^{11} vp/mL in single-use vials, with an extractable volume of 0.5 mL, and dose at 5×10^{10} vp. All participants will receive a single 0.5 mL dosage, typically in the deltoid.
 
Segment I—one dose Segment II—two doses (see protocol)

Duration of Administration	Each dose will be a single dose of Janssen Ad26.CoV2.S vaccine
Reference therapy	No

Statistical Methodology	A chi-square test will be used to assess whether there is a statistically significant difference in the response rate for subjects receiving an additional dose with the Janssen Ad26.CoV2.S vaccine either with immunosuppression reduction (N = 150) or without reduction (N = 150).

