This study is a phase III, prospective, open label clinical trial with one randomized arm. Its goal is to meet the unmet clinical need to provide vaccine induced immunity for our immunocompromised kidney transplant patients after receiving two or more doses of the Pfizer or Moderna COVID-19 vaccine (see Figure below for overview). Subjects will be pre-screened and interested qualified

subjects will be offered participation in this trial and, if applicable, consented. Once consented, serum levels of anti-SARS-CoV-2 spike protein antibody will be obtained. Patients with levels ≥ 250 U/ml will be followed for two years without receiving the Janssen Ad26.CoV2.S vaccine for clinical outcomes (COVID infection, graft and patient survival).

Study Schematic: Augmenting Anti-COVID Immunity In Transplant Recipients Via Heterologous Prime Booster Vaccination With Janssen Ad26.CoV2.S Vaccine

*Clinical endpoints include COVID-19 infection (primary endpoint) and secondary endpoints (hospitalization, infectious complications, patient survival, graft survival, significant AEs related to vaccine or to reduction in immunosuppression, de novo alloantibody)

** Exact cut-off still to be determined

Segment I

Patients with levels >0 but <250 U/ml of anti-SARS-CoV-2 spike protein antibody levels will receive one dose of the Janssen Ad26.CoV2.S vaccine. Their anti-SARS-CoV-2 spike protein antibody levels will be measured at multiple time points after receiving the Janssen Ad26.CoV2.S vaccine. Patients with undetectable anti-SARS-CoV-2 spike protein antibody levels (i.e. with levels = 0) will be randomized 1:1 (stratified by the number of mRNA doses received 2 vs 3) to receive the Janssen Ad26.CoV2.S vaccine and either: 1) continue on their current immunosuppression regimen or 2) have a transient immunosuppression medication adjustment prior receiving the Janssen Ad26.CoV2.S vaccine (described in Section 5.2.1).

Segment II

Patients in Segment I who received Janssen Ad26.CoV2.S vaccine while maintained on their usual immunosuppression medication dosage and did not reach the anti-SARS-CoV-2 spike protein antibody endpoint (≥ 250 U/ml) at 28 days will be offered an additional Janssen Ad26.CoV2.S vaccination. In this segment, immunosuppression will be adjusted (as described in Section 5.2.1)

and anti-SARS-CoV-2 spike protein antibody levels will be assessed at 28 days after the second vaccination with the Janssen Ad26.CoV2.S vaccine as the primary endpoint.

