3.1.1 Segment I

From the screened population, 100 kidney transplant recipients with an anti-SARS-CoV-2 spike protein antibody levels >0 but $<250\text{U/ml}$ (termed low responders) will receive an additional dose of the Janssen Ad26.CoV2.S vaccine. 300 kidney transplant recipients with undetectable anti-SARS-CoV-2 spike protein antibody levels (termed non responders) will receive an additional dose of the Janssen Ad26.CoV2.S vaccine after randomization 1:1 to either a continuation of their current immunosuppression regimen, or after immunosuppression adjustment as defined in Section 5.2.1.

The primary endpoint for Segment I is a SARS-CoV-2 spike protein antibody level $\geq 250\text{ U/ml}$ 28 days after vaccination. Anti- SARS-CoV-2 spike protein antibody levels along with anti-SARS-CoV-2 nucleocapsid antibody levels will be evaluated on days 14, 28, 90 and 180 days. If levels are detectable at Day 180, an additional sample collection will be obtained between one to two years after receiving the Janssen Ad26.CoV2.S vaccine.

- 1) Non-responders (n=300): These are patients who had no antibody response to their initial COVID mRNA vaccination (SARS-CoV-2 spike protein antibody = 0 U /mL). For this randomized portion involving non-responders, we will stratify patients so that we will have equal numbers of patients in each arm who have received 2 doses of mRNA vaccine and equal numbers that have received 3 doses of mRNA vaccine.
 - a. Randomization:
 - i. 150 subjects to receive Janssen Ad26.CoV2.S vaccine.
 - ii. 150 subjects to receive Janssen Ad26.CoV2.S vaccine AFTER immunosuppression adjustment as defined in “Immunosuppression Adjustment” section 5.2.1.
- 2) Low responders (n=100): Patients who had a demonstrable response to COVID mRNA vaccination but were below cutoff (SARS-CoV-2 spike protein antibody 0 to $<250\text{ U/mL}$) will receive the Janssen Ad26.CoV2.S vaccine.

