4.1 Inclusion Criteria

Criteria for Entry into the Study:

- Any kidney transplant recipient from Mayo Clinic who has received at least two doses of the mRNA vaccine (two or more doses of mRNA vaccine-Moderna or Pfizer) and are >28 days after most recent vaccination at the time of spike protein assessment.
- Recipients of a kidney transplant, including those transplanted with other solid organ transplants in addition to the kidney. Subjects may have received more than 1 kidney transplant.
- More than 90 days since any transplant including a kidney transplantation.
- ≥ 18 years of age on the day of consent.

Criteria for Entry into Segment I

- Must have a Roche Elecsys® Anti-SARS-CoV-2 S level of <250 U/mL to be eligible for Segment I.
- Platelet count of >75,000/ μ L on the day of vaccination with the Janssen Ad26.CoV2.S vaccine.
- Contraceptive (birth control) use should be consistent with local regulations regarding the acceptable methods of contraception for those participating in clinical studies.
- Before randomization, participants must be either:

- Not be of childbearing potential
- Of childbearing potential and practicing an acceptable effective method of contraception. Subject must agree to remain on contraception from date of consent until 3 months after the last dose of the Janssen Ad26.CoV2.S vaccine. Use of hormonal contraception should start at least 28 days before the 1st administration of the Janssen Ad26.CoV2.S vaccine. The sponsor-investigator should evaluate the potential for contraceptive method failure (for example, noncompliance, recently initiated) in relationship to the Janssen vaccination. Acceptable effective method a for this study include:
 - Hormonal contraception:
 - Combined (estrogen and progestogen containing) hormonal contraception associated with inhibition of ovulation (oral, intravaginal, or transdermal)
 - Progestogen-only hormonal contraception associated with inhibition of ovulation (oral, injectable, or implantable)
 - Intrauterine device
 - Intrauterine hormone-releasing system
 - Bilateral tubal occlusion/ligation procedure
 - vasectomized partner (the vasectomized partner should be the sole partner for that participant)

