6.1 Segment I

6.1.1 Day - 21 (-30 /+7 Days)

Potential subjects will be identified by review of their medical record. If a participant is identified by review of the report, they will be contacted via the Mayo Clinic portal, the online patient communication system, phone or e-mail (if the potential subject has already contacted the study team in this manner). Study details, procedures, risks, and benefits will be described to patients interested in participation. Subjects will be consented for study participation either via telephone or at Mayo Clinic, depending on patient preference. The participant's medical history, demographics, concomitant medications and therapies, immunosuppression medications and clinical outcomes (current health and graft status) will be collected. Subjects will complete the COVID-19 Surveillance and Evaluation questionnaire (Section 14.6). Relevant medical procedures which are performed as part of the participants clinical care up to 60 days prior to signing of consent, such as clinical laboratory results may be used for determining study eligibility.

Blood for anti-SARS-CoV-2 spike protein antibody and anti-SARS-CoV-2 nucleocapsid total antibody testing will be drawn locally and sent overnight to Mayo Clinic-Rochester Laboratory for

testing. Not all screening procedures need to occur in one day. After consent is obtained, screening procedures can be completed on any day up to the baseline visit.

Patients who meet criteria will be contacted and scheduled to receive the Janssen Ad26.CoV2.S vaccine. They will be required to travel to one of the 3 Mayo Clinic transplant centers to receive the vaccine. There will be 3 groups:

1. Low-responders (n=100)
2. Non-responders (n=300)—Randomized after obtaining evidence that anti-SARS-CoV-2 spike protein antibody levels = 0 U/mL. Patients are stratified by the number of mRNA vaccines they received (2 or more).
 - a. Dosing with the Janssen Ad26.COVID-19 vaccine without immunosuppression adjustment
 - b. Dosing with the Janssen Ad26.COVID-19 vaccine with immunosuppression adjustment.

Subjects randomized to receive immunosuppression adjustment will follow one of the regimens outlined in Section 5.2.1. If randomized to the immunosuppression group, they will be contacted via phone by a physician with instruction on the participant's new immunosuppression regimen.

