We have performed power calculations using several different assumptions regarding the expected outcomes table below. For example, if we expect that the true response rate of 20% of patients without anti-S antibodies at baseline without an adjustment to their immunosuppression will achieve the primary endpoint after receiving the Janssen Ad26.COVID-19 vaccine, then a true response rate of 37% in the patients in the altered immunosuppression group will reject the null hypothesis of an equal response rate with 90% power. Thus, 120 patients will still have low levels (< 250 U/ml) and 30 will have high levels (≥ 250 U/ml). Of the 100 with low levels prior to receiving the Janssen Ad26.COVID-19 vaccine, we expect that >90 will develop high levels.

Response rate in arm with no alteration in immunosuppression	Response rate in arm with alteration in immunosuppression	Power	Significance level (alpha)
20%	60%	1.00	0.05

10%	24%	0.9	0.05
20%	37%	0.9	0.05
30%	48%	0.9	0.05
23%	40%	0.9	0.05
32%	50%	0.9	0.05
41%	60%	0.9	0.05
52%	70%	0.9	0.05
63%	80%	0.9	0.05

Because we expect a true response rate of 20% and 60% in the patients without and with immunosuppression alteration, respectively, we acknowledge that this study is over-powered for the current enrollment targets. If these were the true response rates, 30 patients would be required for each arm to achieve 90% power. Therefore, even if there is drop out and/or misestimation of the response rates within each category then this study will be sufficiently powered for this comparison.

All tests will be carried out using two-side hypothesis tests with a significance level of 0.05 unless otherwise noted.

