6.8 Statistical Methods

In general, univariate descriptive statistics will be calculated, as appropriate for all variables including baseline values for demographic, clinical, and outcome variables. These variables will be summarized across treatment groups as well as strata of baseline antibody levels (none versus low) and compared for possible confounding of the primary and secondary comparisons. For example, what are the univariate and multivariate factors related to the initial good response to mRNA vaccination—data collected at the time of enrollment in all 1200 study subjects. Of additional interest are factors related to response to receiving the Janssen Ad26.CoV2.S vaccine as well as developing COVID infection at 2 years.

The **primary comparison (randomized trial of immunosuppression adjustment)** will focus on a chi-square test of vaccination response between those patients that did not have reduced immunosuppression versus those that did have a change in immunosuppression. Only the patients with a zero (undetectable) antibody level at the time of study enrollment will be compared.

Other analyses will focus on the overall incidence rate of reaching the primary endpoint across all patients or stratified by antibody levels (zero or low) at the time of screening. These analyses will be carried out using one-sample or two-sample chi-square tests. In addition, there is interest if possible confounding variables have any impact on reaching the primary endpoint. These analyses will focus on univariate and multivariate logistic regression models of binary response based on possible confounding variables.

Studying the durability of antibody production will utilize longitudinal analyses such mixed effects models to account for multiple (correlated) observations from the same individual. Assumptions of these models will be assessed through the residual plots.

Finally, we are interested in assessing changes in infection rate and cause-specific mortality during follow-up. We will analyze time to infection or COVID-related death using standard survival analysis procedures such as Kaplan-Meier estimation and Cox regression.

Handling of Missing Data

Queries in the Medidata Rave system will be used to identify outliers as well as missing and inconsistent data entered into the system. An example would be dates that appear out of order such as a death prior to an infection.

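### Randomization is stratified by number of prior mRNA doses, but the primary chi-square test ignores the strata and so may give up a little precision

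*Combined protocol and SAP*

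**What the plan says.** Section 3 (Segment I) randomizes patients with undetectable antibody 1:1, "stratified by the number of mRNA doses received 2 vs 3". Section 3.1.1 gives the purpose: "we will stratify patients so that we will have equal numbers of patients in each arm who have received 2 doses of mRNA vaccine", and likewise for 3 doses. Section 6.1.1 labels the factor differently: "Patients are stratified by the number of mRNA vaccines they received (2 or more". Entry under Section 4.1 requires only that a patient "has received at least two doses of the mRNA vaccine", so it sets no upper limit.

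The primary test is named in two places. The Study Summary says "A chi-square test will be used to assess whether there is a statistically significant difference in the response rate", and Section 6.8 says the primary comparison "will focus on a chi-square test of vaccination response between those patients that did not have reduced immunosuppression" and those who did have a change. Neither mentions the dose strata, and neither names an effect estimate or interval for this comparison. Section 6.8 also plans univariate and multivariate logistic regression on possible confounders, but as a further analysis, and it does not name dose number. The antibody strata in Section 6.8 (zero or low) do not help, because every randomized patient is in the zero group.

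**The concern.** Stratifying the allocation makes the arms alike in dose number. If dose number also predicts response, the true variance of the difference in response rates is smaller than the pooled chi-square assumes. The pooled variance still includes variation between strata that the design has already removed. The test then rejects less often than 5% under the null, has somewhat lower power than a stratified test, and goes with a slightly wide confidence interval.

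What is at stake is efficiency and pre-specification. In an open-label trial, it is also better to settle the choice between an adjusted and an unadjusted primary result before the data are seen.

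**Working it through.** **Inputs from the documents.** 150 per arm, 1:1 allocation, arcsine effect size (Section 6.7); two-sided alpha 0.05 ("All tests will be carried out using two-side hypothesis tests with a significance level of 0.05 unless otherwise noted"); 20% versus 37% as the difference detectable with 90% power ("a true response rate of 37% in the patients in the altered immunosuppression group will reject the null hypothesis"); 20% versus 60% expected, for which 30 per arm is stated to be enough.

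**Not in the documents, so assumed.** The share of patients in each dose stratum (50:50, 70:30 and 30:70 tried) and the response rate in each (control rates averaging 20%, gaps of 0 to 30 points). The odds ratio is common to both strata and set so that the treated arm averages exactly 37% or 60%. Arms are exactly balanced within strata and all 150 per arm are analysed.

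**1. The plan's own figures.** With h = 2·arcsin(√0.37) − 2·arcsin(√0.20) = 0.3805, power = Φ(h·√(150/2) − 1.96) = Φ(3.295 − 1.96) = 90.9%, against 90% stated. For 20% versus 60%, h = 0.8449 and n = 2·((1.96 + 1.2816)/0.8449)² = 29.4, so 30 per arm, as stated.

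**2. Size of the plain test under the null.** The ratio of true to assumed variance is r = Σ w·p(1−p) / [p̄(1−p̄)], and the actual size is about 2·(1 − Φ(1.96/√r)). With equal strata and p̄ = 0.20, the denominator is 0.16:

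- 25%/15%: r = (0.1875 + 0.1275)/2 ÷ 0.16 = 0.984, size 4.8%
- 30%/10%: r = (0.21 + 0.09)/2 ÷ 0.16 = 0.9375, size 4.3%
- 35%/5%: r = (0.2275 + 0.0475)/2 ÷ 0.16 = 0.859, size 3.4%

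**3. Simulation.** 400,000 trials per scenario, chi-square and CMH both without continuity correction, 20% versus 37%:

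| Split | Control strata | Treated strata | Power, chi-square | Power, CMH | Null size, chi-square |
|---|---|---|---|---|---|
| 50:50 | 20/20 | 37/37 | 90.9% | 90.9% | 5.0% |
| 50:50 | 25/15 | 44.3/29.7 | 91.1% | 91.4% | 4.8% |
| 50:50 | 30/10 | 52.0/22.0 | 91.8% | 93.0% | 4.4% |
| 50:50 | 35/5 | 60.8/13.2 | 93.2% | 95.7% | 3.5% |
| 70:30 | 26/6 | 46.9/13.8 | 91.8% | 92.9% | 4.4% |
| 30:70 | 34/14 | 56.1/28.8 | 91.6% | 92.5% | 4.5% |

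CMH size was 4.9% to 5.1% in these scenarios. Independent runs agree to about 0.1 point. At 20% versus 60% both tests had essentially 100% power in every scenario. The 30/10 case implies a between-stratum odds ratio of (0.30/0.70)/(0.10/0.90) = 3.9, and the 35/5 case about 10, which is extreme.

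**4. Confidence interval for the risk difference, 20% versus 37%.** Unstratified half-width: 1.96·√[(0.16 + 0.2331)/150] = 10.0 points. Stratified with equal strata: 1.96·√[0.25·Σ p(1−p)/75], the sum running over the four stratum-by-arm cells:

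- 25/15: Σ = 0.771, half-width 9.9 points
- 30/10: Σ = 0.721, half-width 9.6 points
- 35/5: Σ = 0.628, half-width 9.0 points

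Simulated averages were 9.9, 9.5 and 8.9, against 10.0 unstratified.

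**The case against.** The strongest reply is that the plan chooses between two valid tests. The plain chi-square kept at least 90% power in every scenario run, the difference in proportions is valid either way, and Section 6.7 itself calls the study over-powered for the rates it expects. The larger gains need a strong association between dose number and response. No passage says that dose number still predicts response once every randomized patient has undetectable antibody. All of this stands; it limits the size of the point, not its direction.

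The planned logistic models could also produce a dose-adjusted estimate. That is a partial answer only, since they are not primary and do not name dose number.

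The calculations assume exact balance within strata, whereas Section 6.9 bases the primary analysis on the all-completed population, in which balance may be lost. That is a fair limit on the figures. It is no argument for the plain test: a stratified analysis also adjusts for any resulting imbalance in dose number, though it does not cure the exclusion of non-completers.

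Finally, a stratum of 3 or more doses appears nowhere in the documents, and relabelling could separate the analysis from the allocation. That caution is right and is built into the fix.

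**Conclusion.** The point holds as a small matter of efficiency and pre-specification. The strata used to randomize are not carried into the primary test. If dose number is prognostic, the chi-square is conservative (true size about 4.8% to 4.4% for assumed gaps of 10 to 20 points) and gives up about 0.3 to 1.2 points of power at 20% versus 37%, or about 2.5 points at an extreme 30-point gap. If dose number is not prognostic, the two tests agree, and at the expected 20% versus 60% power does not separate them. These sizes depend on assumed stratum shares and rates; the direction does not. The change is worth making because it is nearly free, was never materially worse in these calculations, and supplies an estimate and interval that the primary comparison lacks. The inconsistent stratum label needs settling whichever test is used: under 2 versus 3, a patient with four or more doses is eligible but has no stated stratum.

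**What to change.** In Section 6.8 and the Study Summary, make the primary analysis a two-sided CMH test at 0.05 stratified by the randomization stratum, reported with the Mantel-Haenszel risk difference and its 95% confidence interval. Keep the unstratified chi-square as a supportive analysis.

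Use one stratum definition that covers every eligible patient, such as 2 versus 3 or more doses, in Sections 3, 3.1.1, 6.1.1 and 6.8. If allocation has already begun, analyse by the stratum actually used to randomize each patient, and state how patients with more than 3 doses were classified.

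The cost is one sentence in each of the two places and one consistent label. The stratum is already needed for randomization, so no patients or data items are added.

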3.4 Primary Study Endpoints

The primary endpoint of all studies is the detection of antiSARS-CoV-2 spike antibody levels ≥ 250 U/ml in serum 28 days after receiving the Janssen Ad26.CoV2.

We have dual primary objectives in this study with the response defined as the following: achieving an anti-SARS-CoV-2 spike protein antibody level ≥ 250 U/ml 28 days after an additional dose with the Janssen Ad26.CoV2.S vaccine.

1. To assess whether an anti-SARS-CoV-2 spike protein antibody level of ≥ 250 U/mL can be achieved 28 days after a dose of the Janssen Ad26.CoV2.S vaccine in kidney transplant recipients who did not form acceptable levels of anti-SARS-CoV-2 spike protein antibody (<250 U/ml but >0 U/mL) after receiving two or more doses of a mRNA vaccine: Pfizer-BioNTech (BNT162b2 vaccine) or Modena (mRNA-1273). This includes any combination of the Pfizer-BioNTech (BNT162b2 vaccine) or the Moderna (mRNA-1273) results in two or more doses of mRNA vaccine. This is not randomized and not controlled.
2. To compare whether a dose of the Janssen Ad26.CoV2.S vaccine can achieve an anti-SARS-CoV-2 spike protein level ≥ 250 U/mL in kidney transplant recipients with no detectable anti-SARS-CoV-2 spike protein antibody after two or more mRNA vaccines. Kidney transplant recipients will be randomized to either maintenance of current immunosuppression or

adjustment in immunosuppression around the time of receiving the Janssen Ad26.CoV2.S vaccine. The number of subjects with anti-SARS-CoV-2 spike protein level ≥ 250 U/mL between the two randomized groups will be compared.

Thus, the ***primary comparison*** for this study is the rate of achieving this endpoint after receiving the Janssen Ad26.CoV2.S vaccine in patients who: 1) had undetectable anti-SARS-CoV-2 spike protein antibody levels after 2 or more doses of mRNA vaccine; and then were 2) randomized to either no alteration in immunosuppression vs alteration in immunosuppression around the time of receiving the Janssen Ad26.CoV2.S vaccine. The power calculations will focus on the difference in the proportion of patients who meet this endpoint between those with no alteration and those with an alteration in immunosuppression.

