3.5 Secondary Study Assessments/Endpoints

- Any response in non-responders: Number and percentage of patients with undetectable anti-SARS-CoV-2 spike protein antibody level after 2 or more doses of mRNA vaccine who receive the Janssen Ad26.CoV2.S vaccine who develop anti-SARS-CoV-2 spike protein antibody levels >0 or <250 at 28 days.
- Good response in low-responders: Number and percentage of patients with anti-SARS-CoV-2 spike protein antibody levels >0 but <250 U/ml after 2 or more doses of mRNA vaccine who receive the Janssen Ad26.CoV2.S vaccine who develop anti-SARS-CoV-2 spike protein antibody levels ≥ 250 at 28 days.
- Segment II. Rate of achieving an anti-SARS-CoV-2 spike protein antibody level ≥ 250 U/ml 28 days after receiving the Janssen Ad26.CoV2.S vaccine in patients who failed to achieve the response in Segment I who received a second dose of the Janssen Ad26.CoV2.S vaccine after adjustment of immunosuppression.
- Durability of anti-SARS-CoV-2 spike protein antibody levels in patients who developed any level of antibody response after receiving the Janssen Ad26.CoV2.S vaccine at 180 days and/or between 1 and 2 years after receiving the Janssen Ad26.CoV2.S vaccine.
- Incidence of COVID-19 infection at 2 years.

Exploratory Endpoints (Mechanistic studies):

Baseline Differences

It is expected that at baseline (prior to receiving the Janssen Ad26.CoV2.S vaccine), when compared to responders, low responders and non-responders will demonstrate no SARS-CoV-2 specific T and B cells and lower mean number of T cell receptors. Non-responsiveness will correlate with lower mean numbers of T and B cells including specific subtypes such as T-helper cells and memory B cells.

Response to Alterations in Immunosuppression

Alterations in immunosuppression will lead to increased number of T and B cells from baseline. Paired t test with each patient serving as their own controls.

Additional Dose with the Janssen Ad26.CoV2.S Vaccine

Compared to those who do not respond, patients who respond to receiving the Janssen Ad26.CoV2.S vaccine will demonstrate new or increased levels of SARS-CoV-2-specific T and B cells. They also will have higher baseline levels of T cells, B cells, serum immunoglobulin levels and T cell repertoire.

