After data has been collected and locked as an analysis dataset, missingness will be assessed for degree as well as randomness. If the amount of missing data is small, incomplete observations will be removed from analyses of interest. On the other hand, imputation using chained equations (MICE) or random forests may be applied in the case of observations that are missing at random.

Multiplicity

There will be only a single analysis of the primary outcome across two treatment groups and therefore multiplicity is not a concern. However, for comparisons of possible confounding variables across treatment groups, multiple testing may give rise to elevated type I error. For these analyses we will consider correcting the p-values via the Benjamini-Hochberg or other methods.

Statistically significant differences on overall comparisons will be explored using multiple pairwise comparisons of each of the (n) groups using Bonferroni correction for multiple comparisons. Mean scores and standard deviation for each group will be calculated. Subsequent multiple comparisons via Tukey's procedure will be set at 0.01 to control Type I error rate.

A Note on the Incidence of COVID 19 at 2 Years

The major reason for the large numbers of patients is to have a reasonable chance of demonstrating a difference in COVID-related complications in responders vs low/non-responders after receiving the Janssen Ad26.COv2.s vaccine. The risk of COVID 19 infections in patients without anti-SARS-CoV-2 spike protein antibody is unknown and the risk of COVID infection going forward in the US also is unknown. Over the past year prior to vaccination programs, the COVID infection rate in our patient population has been approximately 10% per year with death rates of approximately 2% overall per year.

The comparisons here are one-sample comparisons of Kaplan-Meier estimates of the incidence of infection or mortality versus historical incidences of 10% and 2%, respectively.

COVID Infection Rates: Using an assumed 10% infection rate per year as the null hypothesis in the 400 patients that had an undetectable or low mRNA vaccine response, an infection rate of less than 7% will result in 90% power to demonstrate statistical significance by the one-sample log-rank test.

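### Section 6.8 sets multiplicity aside on the ground of a single primary analysis, yet an uncontrolled second objective is also labelled primary, with no null and a success criterion that almost any response would meet

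*Combined protocol and SAP*

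**What the plan says.** **Multiplicity.** Section 6.8, under Multiplicity: "There will be only a single analysis of the primary outcome across two treatment groups and therefore multiplicity is not a concern".

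**Two primary objectives.** Section 3.4: "We have dual primary objectives in this study". The Study Summary and Section 2 list the same two. Objective 1 is Day 28 response (at least 250 U/mL) in low responders, of which Section 3.4 says: "This is not randomized and not controlled". Objective 2 is the same response compared between the two randomized arms of non-responders.

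**One primary comparison.** The Statistical Methodology row of the Study Summary, the end of Section 3.4, the power calculation in 6.7, the analysis in 6.8 and the primary population in 6.9 all point to objective 2.

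**Significance for the other objective.** Section 6.7 says that a 1-2% response would already be significant for the other primary objective and that power there is irrelevant. It then gives a response above 50% in low responders as clinically meaningful. It sets 0.05, two-sided, for all tests unless noted. Section 6.8 puts one- or two-sample chi-square tests by antibody stratum under other analyses.

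**Conflicting labels.**
- Low-responder response is primary objective 1 and also stands in Section 3.5: "Good response in low-responders: Number and percentage of patients".
- COVID-19 infection, in the schematic footnote of Section 3: "Clinical endpoints include COVID-19 infection (primary endpoint) and secondary endpoints". It is secondary in the Study Summary, Section 2 and Section 3.5.
- Segment II response, in Section 3: "28 days after the second vaccination with the Janssen Ad26.CoV2.S vaccine as the primary endpoint". It is secondary in the same three lists.

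**Pairwise rules.** Section 6.8 applies Bonferroni to pairwise comparisons of an unspecified number of groups, and then: "Subsequent multiple comparisons via Tukey's procedure will be set at 0.01 to control Type I error rate".

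**The concern.** The sentence in 6.8 is true of the randomized comparison taken alone. It is not true of a plan with two primary objectives. No section gives a testing order, an alpha split, or a rule that both objectives must succeed.

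What is at stake is the claim the trial may make. If the randomized comparison misses, the plan's wording still allows a report that a primary objective was met, on the strength of an uncontrolled group and a criterion that almost any observed response satisfies. Such a statement would have no error control behind it and would say nothing about immunosuppression adjustment.

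The pairwise rules are a separate and lesser matter. Two procedures at different error levels are prescribed for the same kind of comparison, and nothing says which one decides.

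**Working it through.** **1. The plan's own power figure (Section 6.7).** Inputs: 150 per arm, 20% v 37%, two-sided 0.05, arcsine effect size.

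- h = 2·arcsin√0.37 − 2·arcsin√0.20 = 0.3805
- Power = Φ(h·√(150/2) − 1.960) = Φ(3.295 − 1.960) = 90.9%. Stated: 90%. It reproduces.
- For 20% v 60%, n = 2·((1.960 + 1.282)/h)² = 29.4, so 30 per arm. Stated: 30. It reproduces.

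These figures spend the whole 0.05 on the randomized comparison. If alpha were split between two primaries (0.025 each), power for 20% v 37% would be Φ(3.295 − 2.241) = 85.4%.

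**2. What objective 1 would be tested against.** No null is stated. Section 6.7 supports two readings (n = 100 low responders).

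*Null near 0%, implied by the 1-2% remark.* If the true rate is exactly 0%, no responder can occur, so the type I error is zero. The criterion is nearly automatic at any real response rate: the chance of at least one responder is 1 − 0.98¹⁰⁰ = 86.7% at a true rate of 2% and 1 − 0.95¹⁰⁰ = 99.4% at 5%. Two responders in 100 give an exact 95% interval of 0.2% to 7.0%, which excludes zero and lies far below 50%. The one-sample chi-square named in 6.8 cannot be computed against a null of 0%, because it divides by an expected count of zero.

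*Null of 50%, the plan's mark for clinical meaning.* An exact two-sided 0.05 test needs at least 61 responders: P(X ≥ 61 | 100, 0.5) = 1.76%.

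So success takes one or two responders on one reading and 61 on the other. The plan chooses neither.

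**3. Family-wise error.** Low responders and non-responders are different patients, so independence is reasonable for these two tests.

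| Reading | Calculation | Result |
|---|---|---|
| Objective 1 null near 0% | 1 − 0.95 × 1 | 5% |
| Exact test of 50%, n = 100, favourable tail for objective 1 | 1 − 0.95 × (1 − 0.0176) | 6.7% |
| Two tests, each at a full 0.05, either can support a claim | 1 − 0.95² (bound 0.05 + 0.05) | 9.75% (at most 10%) |

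If both objectives had to succeed, no adjustment would be needed. The plan does not state that rule.

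**4. The two pairwise rules.** The number of groups is not given, so it is assumed here. Tukey is read as family-wise 0.01 with large samples.

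| Groups (assumed) | Pairs | Bonferroni 0.05, per pair | Tukey 0.01, per pair |
|---|---|---|---|
| 3 | 3 | 0.05/3 = 0.0167 | about 0.0036 |
| 4 | 6 | 0.05/6 = 0.0083 | about 0.0019 |

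A pairwise p of 0.005 passes the first rule and fails the second in both rows.

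**The case against.** The strongest reply is that the plan does fix its deciding test. Section 3.4 declares two objectives and then closes by naming the randomized comparison as the primary one, and the Study Summary, 6.7, 6.8 and 6.9 agree. The sentence in 6.8 describes that comparison accurately. This stands. A reader might infer that the plan leaves open which result decides the trial, and the documents do not support that.

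It can also be said that no second confirmatory test is planned. The one-sample tests are listed under other analyses, objective 1 is openly uncontrolled, and 6.7 says low responders were included to develop data on a treatment option. This stands in part: a planned second primary test at 0.05 is an inference. But 6.7 does call it a primary objective and does speak of its statistical significance.

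Section 6.7 is also muddled about whom the 1-2% remark covers. It describes patients without antibodies, gives the low-responder range in brackets, and then turns to non-responders. The bracket and the words *other primary objective* match objective 1, and the muddle is one more reason to rewrite the paragraph.

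A reader might count four primary tests, adding Segment II response and COVID-19 infection, and reach 1 − 0.95⁴ = 18.5%. That figure should not be used. It assumes independence, although Segment II patients come from Segment I and infection is assessed in the same 400 patients. The bound would be 20%, not 18.5%. Segment II has no null and no specific test. The labels in Section 3 can be read as primary within a segment or among clinical endpoints, and the formal lists make both secondary.

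Finally, the Bonferroni and Tukey paragraph is not tied to the binary primary endpoint. It speaks of mean scores and follows the remarks on confounders, so it cannot change the two-arm primary test.

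**Conclusion.** The concern holds in a limited form. The multiplicity statement in 6.8 contradicts the dual primary objectives in Sections 2 and 3.4 and the significance language in 6.7. The randomized comparison remains the plan's primary comparison, and its power figures are sound. The weakness is that a second, uncontrolled objective with a primary label, no null and an almost automatic criterion could be reported as met when the randomized test fails.

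The size is conditional: about 5% family-wise error with a null near 0%, about 6.7% with an exact test of 50% in 100 patients, and at most about 10% if both tests run at a full 0.05 and either can support a claim. At the lowest figure the problem is not alpha inflation but a primary claim that means little. The conflicting pairwise rules affect exploratory comparisons only.

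This should be corrected before analysis, but it does not threaten the design.

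**What to change.** 1. Name the randomized comparison in non-responders as the sole confirmatory primary endpoint, at two-sided 0.05. The sentence in 6.8 then becomes true.
2. Report low-responder Day 28 response as secondary or descriptive, with an exact 95% confidence interval set against the plan's own mark of more than 50%. It already stands in Section 3.5.
3. Delete the statement in 6.7 that a 1-2% response would be significant, and say clearly which population that paragraph covers.
4. Make the labels agree in the Study Summary, Section 2, Section 3 (COVID-19 infection and Segment II), 3.4, 6.7 and 6.8.
5. Replace the Bonferroni and Tukey text with one rule, such as Holm at 0.05, for any exploratory pairwise comparisons, and name the groups.

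The cost is wording. Sample size and procedures do not change, and the randomized comparison keeps its full alpha and about 90% power for 20% v 37%. The downside is that the low-responder result loses its primary label. If the sponsor prefers to keep both primaries, it needs a stated null for objective 1 and a testing rule; an equal alpha split would lower that power to about 85%.
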